## 11 DEFINITION OF ADVERSE EVENTS

### 11.1 Adverse Event (AE)

An Adverse Event is defined as any untoward medical occurrence, unintended disease or injury or any untoward clinical signs (including an abnormal laboratory finding) in subjects, users or other persons, whether or not related to the investigational medical device.

Adverse Event Identification: A condition that is one of the following:

1. A unique symptom or event that is a change from the subject's baseline status
2. A series of symptoms or events that can be categorized as a single entity based on definitions found herein
3. A specific diagnosis responsible for a clinical change
4. A worsening or exacerbation of a pre-existing condition

### 11.2 Serious Adverse Event (SAE)

An adverse event is considered to be a serious adverse event (SAE) when the subject outcome is any of the following:

1. Death
2. Life-threatening
3. In-patient hospitalization or prolongation of an existing hospitalization
4. Persistent or significant disability/incapacity
5. Substantial disruption of a person's ability to conduct normal life functions, i.e. the adverse event resulted in a significant, persistent or permanent change, impairment, damage or disruption in the subject's body function/structure including chronic diseases, physical activities and/or quality of life
6. Congenital anomaly or birth defect
7. Required medical or surgical intervention to prevent permanent impairment of a body function or damage to a body structure
8. If the AE does not fit the other outcomes, but the event may jeopardize the health of the subject or require medical or surgical intervention (treatment) to prevent one of the

outcomes listed above

An SAE may or may not be related to the study procedure.

*Note: A planned hospitalization for a pre-existing condition, or a procedure required by the protocol without serious deterioration in health, is not considered a serious adverse event.*

### **11.3 Unanticipated Adverse Device Effect (UADE)**

Any serious adverse effect on health and safety or any life-threatening problem or death caused by, or associated with, a device, if that effect, problem, or death was not previously identified in nature, severity, or degree of incidence in the investigational plan or application (including a supplementary plan, related documentation or application), or any other unanticipated serious problem associated with a device that relates to the rights, safety, or welfare of subject.

### **11.4 Serious Adverse Device Effect (SADE)**

An adverse device effect that has resulted in any of the consequences characteristic of a serious adverse event.

### **11.5 Unanticipated Serious Adverse Device Effect (USADE)**

A serious adverse device effect which by its nature, incidence, severity or outcome, has not been identified in the current version of the risk analysis report.

### **11.6 Device Technical Observation**

An observation of a medical device with respect to its identity, quality, durability, reliability, safety or performance. Device deficiencies that did not lead to an AE but could have led to a medical occurrence will be reported, under the following circumstances:

1. if either suitable action had not been taken,
2. if intervention had not been made, or
3. if circumstances had been less fortunate.

### **11.7 Adverse Event Classification and Reporting Requirements**

Adverse events will be assigned an attribution according to the Investigator's believed primary cause. Events will be categorized by relationship to the Investigational Device, Insertion Procedure, concomitant medications, pre-existing condition, intercurrent condition, intercurrent intervention, or other.

Adverse events should be classified according to their underlying cause, if known (e.g., fever resulting from infection should be reported as "infection"). Symptoms related to a diagnosis should not be reported as separate AEs. In the above example, fever is a symptom caused by infection and should be reported as infection only.

Concomitant AEs that are unrelated (in the clinician's judgment) should be reported as separate events.

AE determination is based on three levels of evidence:

Level 1 – final diagnosis

[figure not shown]
Level 2 – signs

Level 3 – symptoms

Every effort should be made to collect Level 1 evidence of any AE. If an AE has all three levels of evidence, the AE should be reported only once at the highest level of severity, which is the final diagnosis (Level 1). A single AE should not be reported as multiple AEs based on separate symptoms and signs.

In cases where a diagnosis is not possible, AE determination should be based on the next highest level of evidence (i.e., Level 2: signs), followed by symptoms (Level 3), if symptoms are all that are available to the investigator.

A corrective action (e.g. catheterization) itself is not an AE but the reason of the catheterization may be an AE. The AE determination always should be based on the reason that a corrective action was taken. Note: there may be multiple signs or symptoms representing only one AE.

**Figure 11-1: AE Determination and Outcome Flowchart**

The AEs in the study may be further coded by Medical Dictionary for Regulatory Activities (MedDRA) and graded according to Common Terminology Criteria for Adverse Events (CTCAE) for the purpose of regulatory reporting or publication.

## 11.8 Reporting of all Adverse Events

The signs, symptoms and sequelae of an underlying AE should not be reported as separate AEs.

All AEs must be documented on an eCRF. All AEs also must be described by (a) duration (start and resolution dates); (b) adjudicated for severity; (c) relationship to the study device; (d) action taken to resolve the event; (e) outcome of the event; and (f) whether or not such event is considered to have been serious. Additional information, such as procedural notes, treatment notes, or a signed clinical summary, may be required as supporting documentation for the reported AE.

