**Table 7-1: Major Risks for the Connected Catheter**

Risk	Description
Urinary Tract Infection (UTI)	UTI is defined in this protocol as bacteriuria $\geq 10^5$ CFU per mL, plus at least one NIDRR consensus-defined symptom. If infection is suspected, appropriate diagnostic and therapeutic measures should be taken.
Asymptomatic Bacteriuria	The presence of bacteria in the properly collected urine of a patient that has no signs or symptoms of a urinary tract infection.
Bladder Spasms	When the bladder muscle squeezes suddenly without warning, causing an urgent need to release urine. The spasm can force urine from the bladder, causing leakage.
Dysuria	Pain experienced while urinating. Dysuria can be caused by UTI, inflammation of the LUT, sexually transmitted diseases, and more. The operation of the device should not cause pain while voiding. If this occurs, a clinician should evaluate the subject to determine the likely cause and follow the standard of care. If necessary, the device may be removed.
Genitourinary pain	Initial discomfort may occur when first using the device. Pain should be properly evaluated by a clinician and the cause(s) identified. Genitourinary pain can have many causes unrelated to the device itself ranging from enlarged prostate to fibromyalgia to infection. The proper standard of care should be followed once the cause(s) are identified.

Risk	Description
Hematuria	Blood in the urine may be caused by LUT injury, UTI, kidney or bladder stones, enlarged prostate, the device itself (from insertion, removal, migration, improper sizing), and more. During initial use of the device minor hematuria may be observed. If it continues or worsens, then follow the standard of care to diagnose and alleviate the symptom.
Stricture	Hardening of the tissue. May be caused by frequent catheter use and/or false passage.
Urethral Trauma	False passage may be associated with improper and/or frequent catheter use.
Urinary Incontinence	Leaking may occur through or around the catheter if the bladder spasms, or the catheter valve is not closed properly.
Urinary retention	If patient is unable to empty the bladder, then Urinary Retention may occur.
Discomfort	Discomfort is often associated with frequent catheterization.

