### **8.6 Secondary Endpoints**

The following secondary endpoints will provide additional characterization of the Connected Catheter in the treatment of chronic Urinary Retention and to support potential labeling claims.

1. Successful device insertion, anchoring, and removal
2. Successful sealing of the Connected Catheter valve
3. Quality of life improvement as measured by SCI-QOL Survey and other surveys
4. UTI occurrence rate
5. Lower Urinary Tract injury rate

These endpoints will be analyzed with descriptive statistics and nominal 95% confidence interval.

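### Section 11.8 bars separate reporting of sequelae, so a new diagnosis that follows an earlier AE gets no record of its own and may go uncounted

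*Combined protocol and SAP*

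**What the plan says.** Section 11.8 sets the rule: "The signs, symptoms and sequelae of an underlying AE should not be reported as separate AEs". Section 11.7 leans the same way. It says "Adverse events should be classified according to their underlying cause, if known", and the only events it expressly separates are unrelated ones: "Concomitant AEs that are unrelated (in the clinician's judgment) should be reported as separate events". Its one worked example, however, folds a symptom (fever) into a diagnosis (infection). It does not fold one diagnosis into another.

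Other sections treat a second diagnosis as an event in its own right. Section 11.1 gives as a ground for an AE "A specific diagnosis responsible for a clinical change". Section 11.9 lists false passage (item 3), scarring (15), systemic infection (16), urethral stricture (19) and UTI (20) separately. Table 7-1 says of stricture: "May be caused by frequent catheter use and/or false passage".

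The rates at issue are the device-related SAE rate (primary safety, synopsis and Section 10.3), the UTI occurrence rate and the "Lower Urinary Tract injury rate" (Section 8.6, endpoints 4 and 5). The protocol does not say which form feeds each rate, or whether each counts men or events.

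**The concern.** Folding signs and symptoms into their diagnosis is ordinary good practice. A sequela is different: it can be a new diagnosis with its own onset, seriousness and cause. The protocol names a causal pair (false passage, then stricture), lists both members as AEs, and then tells sites not to report the second. Two sites could record the same clinical course differently, each able to point to protocol text.

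Any error runs one way, towards fewer recorded harms. Section 11.8 collects dates, relationship to the device, outcome and seriousness per AE, so a sequela without a record has none of these. The SAE report in Table 14-1 and the adjudication in Section 16.1 both depend on the event being identified as serious.

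**Working it through.** There is no figure in the plan to reproduce. The check sets the sections side by side, then illustrates the size.

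**1. Three courses under the literal rule.** In each, two diagnoses occur. Section 11.8 gives one AE record if the investigator judges the second a sequela; Sections 11.1 and 11.9 would give two.

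| Course | Per-event AE count | Rate that could change |
|---|---|---|
| A. False passage, later stricture | 1 instead of 2 | Per-man injury rate unchanged, since false passage is already an injury; a per-event injury rate falls |
| B. Lower urinary tract injury, later UTI | 1 instead of 2 | UTI rate, if the UTI is captured only through AE review |
| C. Non-serious UTI, later systemic infection with hospitalization | 1 instead of 2 | Device-related SAE rate, if the UTI record is not regraded as serious |

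**2. Where AE review is the main scheduled capture.** Table 9-2 ticks the UTI assessment, and the weekly assessment that contains the urethral injury check, for Device Tolerability Screening and the Test Phase. It ticks neither for Follow-Up or Unscheduled visits. Follow-Up has phone screening and AE review. Unscheduled visits have AE review, vital signs, voiding volume and medications, with further tests at the investigator's discretion (Section 9.6). By the synopsis, follow-up is 2 of the 7 weeks per man. Sequelae come after the first event, so these windows matter.

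**3. Route of a serious sequela into the SAE rate.** Section 11.2 defines an SAE by the subject's outcome, and Section 11.8 puts outcome and seriousness on every AE. The earlier AE can therefore become serious. No visible text requires a non-serious or resolved AE to be reopened or regraded, and the sequela has no relatedness assessment of its own if the earlier AE was attributed to something other than the device.

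**4. Illustration of one lost SAE.** Section 8.8 expects 24 men to try the device. This agrees with its 16 evaluable men: 24 × (1 − 0.33) = 16.08. The number of events is an assumption. Exact (Clopper-Pearson) 95% intervals:

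- 1 of 24: 1/24 = 4.2%. Lower limit 1 − 0.975^(1/24) = 0.1%; upper limit, the 97.5th percentile of Beta(2, 23), = 21.1%.
- 0 of 24: 0%. Upper limit 1 − 0.025^(1/24) = 14.2%.

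Section 10.3 gives 60 as the number who tested the device, which does not agree with 24. With 60, the same change is from 1.7% (0.0 to 8.9%) to 0% (0 to 6.0%).

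**The case against.** A reader might infer that the rule removes later injuries and infections from endpoints 4 and 5 outright. The documents do not support that. No section says these endpoints come from AE records. Section 9.4 lists urinary tract injury and adverse events as separate items at each Test Phase appointment, Table 9-2 schedules UTI assessment in both device-use phases, and the protocol's UTI definition (culture threshold plus symptom) does not depend on what came before. This stands for the device-use visits. It does not cover the Follow-Up Phase or unscheduled visits, although Section 9.5 does allow a clinic appointment if a phone call raises a problem.

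A reader might also infer that serious sequelae necessarily drop out of the SAE rate. They need not: Sections 11.2 and 11.8 together let a hospitalization make the earlier AE serious, and a site applying the SAE definition with care would do so. What is missing is an explicit instruction.

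A UTI after an injury is not automatically its sequela; the investigator would have to judge it so. Sections 11.1 and 11.9 support separate reporting. That is fair, but it shows that the sections conflict, not that the conflict is resolved. Section 11.1 also makes an AE of "A worsening or exacerbation of a pre-existing condition", without saying whether an event that began during the study counts as pre-existing.

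Finally, Figure 11-1, the AE determination and outcome flowchart, is not shown in the text available and may address progression. The safety and secondary endpoints are descriptive only, so no hypothesis test is affected.

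**Conclusion.** The point holds in limited form. Section 11.8 conflicts with Sections 11.1 and 11.9 and Table 7-1. Read literally, it makes per-event AE counts too low. It may cause UTIs or injuries first found in follow-up or at unscheduled visits to be missed in endpoints 4 and 5, and a serious sequela to be missed in the device-related SAE rate if the earlier AE is not regraded.

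Bias in any endpoint is possible, not demonstrated. The documents give no event rates, so any percentage put on a UTI shortfall would rest wholly on assumed inputs. The change from 4.2% to 0% assumes 24 treated men, one such SAE, and a site that does not regrade. For false passage followed by stricture, a per-man injury rate would not change. The conclusion on regrading rests on the visible text, without Figure 11-1.

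**What to change.** In Section 11.8, delete 'and sequelae' (adjusting the grammar), so that the rule covers only signs and symptoms of the same diagnosis, in line with the example in Section 11.7. State that a new diagnosis arising from an earlier AE is recorded as its own AE, linked to the first, with its own onset date, seriousness and relatedness.

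In Sections 8.6 and 10.3, state that endpoints 4 and 5 count every UTI meeting the protocol definition and every lower urinary tract injury, whatever preceded it, from visit assessments and AE records together. State whether each rate is per man or per event; in per-man rates each man counts once, so linked records are not double counted.

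The cost is a few sentences and a link field on the AE eCRF. The downside is a few more AE records and possibly slightly less favourable rates. Clinical management does not change.

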### 11.8.1 Device and Procedure-Related Adverse Event

A description of how an AE relates to the study procedure will be reported on the Adverse Event eCRF and starts from the first use of the device and be determined by the Investigator using the following definitions:

- **Definite:** The AE follows a reasonable temporal sequence from the time of the first insertion procedure, which includes AEs that occur during the index procedure or during the follow-up period.
- **Probable:** The AE follows a reasonable temporal sequence from the time of the first insertion procedure, and the possibility can be excluded that factors other than the index procedure, such as underlying disease, concomitant drugs, or concurrent treatment caused the AE.
- **Possible:** The AE follows a reasonable temporal sequence from the time of the first insertion procedure and the possibility of insertion procedure involvement cannot be excluded. However, other factors such as underlying disease, concomitant medications, or concurrent treatment are presumable.
- **Unlikely:** The AE has an improbable temporal sequence from the time of the first insertion procedure, or such AE can be reasonably explained by other factors, including underlying disease, concomitant medication, or concurrent treatment.
- **Not related:** The AE has no temporal sequence from the time of the first insertion procedure, or it can be explained by other factors, including underlying disease, concomitant medication, or concurrent treatment.

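### In 11.8.1 'Definite' is easier to meet than 'Probable' and the two lowest grades overlap; no visible text says which scheme or grades define a device related SAE

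*Combined protocol and SAP*

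**What the plan says.** The Synopsis names the rate of device related SAEs as the primary safety endpoint. Section 10.3 analyses it with descriptive statistics and nominal 95% confidence intervals, without a hypothesis test, using SAEs from all treated subjects. Section 8.5.2 words it more widely, as adverse events and SAEs related to use of the device.

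Three places deal with causality.

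- **11.7** assigns each event one primary cause, as the investigator believes it to be: "Events will be categorized by relationship to the Investigational Device, Insertion Procedure, concomitant medications, pre-existing condition", and so on. Device and insertion procedure are separate categories.
- **11.8, item (c)** asks for the relationship to the study device.
- **11.8.1** gives five grades, which the investigator must apply as defined. Its lead-in refers to the procedure: "A description of how an AE relates to the study procedure will be reported on the Adverse Event eCRF".

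The grades in 11.8.1 read as follows.

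- *Definite* rests on timing alone: "The AE follows a reasonable temporal sequence from the time of the first insertion procedure, which includes AEs that occur during the index procedure". Events in follow-up are covered too, and there is no condition on other causes.
- *Probable*: the same timing, "and the possibility can be excluded that factors other than the index procedure, such as underlying disease", medication or other treatment, caused the event.
- *Possible*: the same timing, and "the possibility of insertion procedure involvement cannot be excluded", although other factors are presumable.
- *Unlikely*: improbable timing, "or such AE can be reasonably explained by other factors, including underlying disease, concomitant medication, or concurrent treatment".
- *Not related*: no temporal sequence, "or it can be explained by other factors, including underlying disease, concomitant medication, or concurrent treatment".

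Section 16.1 has the Independent Research Monitor adjudicate safety data under the protocol's own guidelines.

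**The concern.** A causality scale should give each event one grade, and a higher grade should need stronger evidence. Here the top grade needs less evidence than the one below it, and an available alternative explanation opens both of the lowest grades whatever the timing. Two raters could give the same SAE opposite grades and both follow the text.

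The wording also sits awkwardly with the endpoint. The grades refer to the study, index or first insertion procedure, while the endpoint concerns the device, which is replaced weekly. At stake is the numerator of the primary safety rate. If the 11.8.1 grade decides entry to it, the rate depends on which compliant grade the rater picked.

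This can arise in practice. Table 7-1 lists infection, stones, enlarged prostate and the device itself among the causes of hematuria, and says that genitourinary pain has many causes unrelated to the device.

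**Working it through.** The plan gives no expected SAE rate and no relatedness cut-off, so there is no figure to reproduce. The check is a comparison of the definitions.

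**Step 1. Reduce each grade in 11.8.1 to its tests.**

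| Grade | Test |
|---|---|
| Definite | reasonable timing |
| Probable | reasonable timing AND other causes excluded |
| Possible | reasonable timing AND procedure not excluded, other factors presumable |
| Unlikely | improbable timing OR reasonably explained by other factors |
| Not related | no temporal sequence OR explained by other factors |

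**Step 2. Top of the scale.** Probable and Possible each contain the whole Definite test plus something more. Any event that meets either one also meets Definite.

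**Step 3. Bottom of the scale.** The second limbs of Unlikely and Not related differ only by an adverb. An event that other factors explain meets both, whatever its timing.

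**Step 4. The two together.** A well-timed SAE that other factors can explain meets Definite (timing), Unlikely (explanation) and Not related (explanation). If involvement of the procedure cannot be excluded, it also meets Possible.

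**Step 5. What is sound.** Probable (other causes excluded) and Possible (other causes presumable) are separate and correctly ordered. So are the timing limbs of Unlikely (improbable) and Not related (none).

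**Step 6. Link to the endpoint.** The Synopsis, 8.5.2, 10.3, 11.7, 11.8, 11.8.1 and 16.1 do not state which scheme or which grades define a device related SAE. Nor do they say whether the investigator's or the monitor's rating is used, or whether the rate is per subject or per event.

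**Step 7. Scale of one reclassification.** Assume a rate per subject, x/n, with exact (Clopper-Pearson) 95% intervals. Section 8.8 expects 24 subjects to reach device tolerability screening, while 10.3 speaks of 60 who tested the device. That conflict is a separate matter, so both are shown.

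| n | x = 0 | x = 1 | Shift |
|---|---|---|---|
| 24 | 0% (0 to 14.2%) | 4.2% (0.1 to 21.1%) | 1/24 = 4.2 points |
| 60 | 0% (0 to 6.0%) | 1.7% (0.04 to 8.9%) | 1/60 = 1.7 points |

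These figures show how much one event weighs. They do not predict how often grades will differ.

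**The case against.** The best reply is that 11.8.1 may not feed the endpoint at all. 'Device related' could be read as the Investigational Device category in 11.7, or as item (c) of 11.8, and then the overlap in 11.8.1 would leave the rate unchanged. "Figure 11-1: AE Determination and Outcome Flowchart" may also hold a rule, and its content is not shown. This stands, and it makes the effect on the rate conditional. It does not repair the definitions.

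Sections 11.8.2 and 11.8.3 direct events tied to medication or a pre-existing condition, and not specific to the device, to their own categories. That narrows the overlap in practice, but leaves the five grades as written and worsened pre-existing conditions to case-by-case judgment. A single monitor improves consistency, but 16.1 has that monitor work from the same protocol guidelines.

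The consequence is also limited. There is no safety test or threshold, 14.7 requires SAEs to be reported to the sponsor whatever their relatedness, and in a study this small each SAE can be listed.

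Two stronger readings are tempting. A reader might infer that the whole scale is disordered. It is not: only Definite is out of place, and only the explanation limbs of the two lowest grades collide. A reader might also infer that the plan is silent on SAEs caused by insertion or removal. That goes too far, because 8.5.2 speaks of use of the device and 9.2.2 describes use as insertion, voiding and removal. Read together they point to inclusion, though no rule says so.

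**Conclusion.** The definitions in 11.8.1 are faulty as written: Definite is weaker than Probable and absorbs both Probable and Possible, and Unlikely and Not related overlap. Confidence here is high, because it follows from the text alone.

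The effect on the primary safety rate is conditional, with moderate confidence. It assumes that the 11.8.1 grade feeds the numerator and that Figure 11-1 does not settle the matter. On that footing one SAE can properly be counted or left out, which for a per-subject rate is worth 4.2 points at 24 subjects or 1.7 at 60.

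A reader might infer that the primary safety result is invalid or that a conclusion could be reversed. The documents do not support that: the analysis is descriptive, no threshold is set, and they give no basis for estimating how often raters would disagree. The point should be corrected before the data are analysed.

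**What to change.** **In 11.8.1**, keep the five labels and judge them against any device use (insertion, wear, voiding or removal), not only the first insertion. Apply them in this order and take the first that is met:

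1. *Not related*: onset before any device use, or another cause established as the full explanation.
2. *Unlikely*: another cause not established, but more likely than the device or procedure.
3. *Definite*: reasonable timing and other causes excluded.
4. *Probable*: reasonable timing, other causes not excluded but less likely.
5. *Possible*: all remaining events, including improbable or unknown timing with no more likely other cause.

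For a worsened pre-existing condition, onset should mean onset of the worsening. Every event then receives exactly one grade, and an SAE with other causes excluded but improbable timing stays in the count.

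**In 10.3**, define a device related SAE as one that the Independent Research Monitor adjudicates as Definite, Probable or Possible in relation to the device or its insertion or removal, in line with the reference to use in 8.5.2. Report subjects with at least one such SAE among all treated subjects. Add Definite plus Probable as a sensitivity analysis, and list the SAEs where the investigator's grade differs. Use the 11.7 categories only for a descriptive split. If Figure 11-1 already holds a counting rule, bring it into line.

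**Cost:** EC/IRB review of the wording (14.8.2), an eCRF relabel, and brief retraining of site staff and the monitor. There is still one grade per event. The stated rate may be somewhat higher once Possible and procedure-related SAEs are counted; the documents do not allow the size to be estimated.
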